6.2.1. Maintenance Dose for Study Drug

The maintenance dose for study drug is defined as the study drug dose with which the subject is last treated before the Exit DBPCFC or EOT (whichever occurs earlier) and tolerated for at least 2 weeks.

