6.2.3. Study/Treatment Period

The study period is the time from the date a subject or parent signed the informed consent/assent to the last day of follow-up. It includes the screening period, treatment period, and follow-up period (only for subjects who do not participate in the OLE study).

Screening Period

The screening period will be up to 12 weeks, including Screening DBPCFC(s) and other screening assessments. The first day of the screening period is the date of informed consent/assent. The last day of the screening period is the day before the date of first dose of study drug. If the subject is re-screened, the duration of the re-screen period must be within 12 weeks, even though some of the food challenges may have been conducted earlier.

Treatment Period

The treatment period will be up to 50 weeks, including 40 weeks of treatment plus up to 6 weeks for Exit Food Challenge/Week 40 (this period may be extended to up to 8 weeks if a subject requires > 6 food challenges) and up to 4 weeks of continued blinded study treatment through EOT. The treatment period will consist of pre-maintenance (including Baseline and updosing portions), maintenance, Exit Food Challenge/Week 40 Visit, and EOT as described in Section 3.1. Pre-maintenance, maintenance and Exit Food Challenge/Week 40 Visit durations will be variable per subject.

The start of the pre-maintenance period is marked by the date of Day 1 (Baseline). The start of the maintenance period is marked by the date of first dose of the sequence of maintenance doses administered closest to the first Exit Food Challenge/Week 40 Visit assessment. The Exit Food Challenge/Week 40 Visit period starts with the date of the first Week 40 Visit assessment and the end of this period is the last day of the last DBPCFC.

Follow-Up Period

Subjects who are ineligible for or do not wish to continue to the OLE study will receive instruction by the investigator about withdrawal from study drug and attend a Follow-Up Visit. The follow-up period will be 14 days from the EOT Visit. The beginning of the follow-up period is marked by the date of the EOT Visit + 1.

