6.2.6. Treatment Exposure

6.2.6.1. Exposure Duration

Subject exposure data are not collected on the study electronic case report form (eCRF). Rather they come from 2 external sources:

- Study drug_accountability (in-clinic) data from Suvoda IRT system.
- Subject daily dosing diary data (non-clinic data) via mobile application (mApp) managed by AiCure. This data will be sent directly to Alladapt for exploratory analysis and are not planned to be included in the CSR of this study

The main calculation of exposure will be based on in-clinic dosing data and the dose level of the dispensed study drug from Suvoda IRT system.

Exposure Duration: Overall Treatment Period

The overall exposure duration (in days) is defined as [Last dose date of treatment – First dose date of treatment + 1].

A combination of the data from the EOT eCRF and the dose information from Suvoda IRT will be used to determine the date of last dose of treatment. For analysis purposes, the date of last study drug administration on the EOT eCRF will be used as the analysis date of last dose date.

Exposure Duration: By Dose Level

At each dose level within the treatment period, the exposure duration (in days) is defined as [Last Dose Date – First Dose Date + 1]. For any subject who has non-continuous dosing at the same dose level due to down dosing, the durations of the individual non-continuous intervals of such dosing are defined as [Last Dose Date of Interval – First Dose Date of Interval +1]. The exposure in days for such subjects at a given dose level would be the sum of the lengths of the individual non-continuous dosing intervals in days for all such non-continuous dosing.

Exposure Duration: Pre-maintenance

The exposure duration of pre-maintenance is anticipated to be of variable length depending on how quickly subjects are able to reach their randomized target dose or maintenance dose.

The exposure duration of pre-maintenance dosing (in days) is defined as [(The day prior to first dose of the sequence of maintenance doses administered closest to the first Exit Food Challenge/Week 40 Visit assessment) – (First dose date of treatment from Baseline Visit) + 1].

Exposure Duration: Maintenance

The exposure duration of the maintenance dosing is defined as [(Date of last maintenance dose before the Exit Food Challenge/Week 40) - (Date of first dose of the sequence of maintenance doses administered closest to the first Exit Food Challenge/Week 40 Visit assessment) + 1].

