- **Maintenance Period:** This period commences just after the Updosing ends. The maintenance dose will be received throughout this period. The start date for this period will be the date of first dose of the sequence of maintenance doses administered closest to the first Exit Food Challenge/Week 40 Visit assessment. The end date of this period will be one day just before the first Week 40 Visit assessment or early termination date (whichever is the earliest) for the subjects discontinued the study during the Maintenance Period. The visits, dates, and data corresponding to this period will be the visits, dates, and data from each data domain that falls into the start and end dates of this period. For occurrence datasets such as adverse events and concomitant medications, the events or medications recorded with the start dates that falls into the start and end dates of this period, will be classified into this period. If the duration of these events span multiple periods, they will be considered ongoing safety events.
If the subject exits the study without achieving a maintenance dose, then a flag will be set to denote that the subject did not achieve a maintenance dose during the study. Subjects who achieve a maintenance dose will have the date/visit of the first dose of the maintenance dose recorded in the database as the first dose of maintenance dose of study drug.
- **Exit Food Challenge/Week 40 Visit:** The Exit Food Challenge/Week 40 Visit will be performed over multiple visits for up to 6 weeks of daily dosing of study drug (this period may be extended to up to 8 weeks if a subject requires > 6 food challenges). Daily dosing will occur during this period except when withhold purposely, e.g., during the day of a DBPCFC. Although this portion potentially spans over a 6 week period (this period may

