7.8.3.10. Maintenance Dose for Study Drug

The maintenance dose (mg/day) will be summarized by treatment group using descriptive statistics (median, min, max, and Q1:Q3). The number and percentage of subjects whose maintenance dose is 50, 100, 200, 400, 700, 1000, 1500, 3000, or 4500 mg/day will be provided as well. If a subject exits the study prior to achieving a dose of at least 50 mg, then the maintenance dose will be set to missing.

The time to achieving the maintenance dose level is defined as [(first dose date of maintenance dose) – (first dose date of study drug) + 1]. The maintenance dose for these individuals can be determined once the subject has started the exit challenge procedure (i.e. maintenance is the week 38 dose level), reached the target dose for their randomized treatment group or discontinued the study. The time to achieving first maintenance dose will be presented for the treatment period using Kaplan-Meier (KM) method. Subjects who do not reach a maintenance dose will be censored at the date of their last study drug dose. KM curves will be plotted separately for the pooled placebo, low-dose and high-dose groups. A similar method will be repeated for time to achieving target dose level (1500 mg/day for low-dose and 4500 mg/day for high-dose) as maintenance dose.

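### The time-to-maintenance curve counts a subject who leaves while still updosing, after 14 days on a last dose of 50 mg or more, as having reached maintenance

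*SAP*

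**What the plan says.** SAP 6.2.1 takes as maintenance dose the dose with which the subject is "last treated before the Exit DBPCFC or EOT (whichever occurs earlier) and tolerated for at least 2 weeks". For a completer, EOT follows the last Exit DBPCFC, so the EOT alternative matters only for subjects who stop before the exit challenge. SAP 7.1 confirms that the End of Treatment form also records early terminations.

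SAP 7.8.3.10 says the maintenance dose can be determined once the subject has started the exit challenge, "reached the target dose for their randomized treatment group or discontinued the study". If the subject leaves "prior to achieving a dose of at least 50 mg, then the maintenance dose will be set to missing". The censoring rule reads: "Subjects who do not reach a maintenance dose will be censored at the date of their last study drug dose". The event time runs from first study dose to first dose at the maintenance level.

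Elsewhere maintenance has a narrower meaning. Protocol 4.1 and SAP 3.1 describe it as the stage at which no more updosing is planned, and SAP 6.4.3 says of the Maintenance Period: "This period commences just after the Updosing ends". SAP 6.2.3 and 6.4.3 start that period on the "date of first dose of the sequence of maintenance doses administered closest to the first Exit Food Challenge/Week 40 Visit assessment". Section 6.4.3 ends it on the day before Week 40 or at the "early termination date (whichever is the earliest) for the subjects discontinued the study during the Maintenance Period".

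**The concern.** Protocol 6.5.1 schedules a new level every 2 weeks, so one completed updosing step can satisfy the 2-week condition in SAP 6.2.1. A child who completes a step partway up the ladder and then withdraws has not reached maintenance in the protocol's sense, yet the SAP rule assigns a maintenance dose and an event.

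The direction of the error matters more than its size. A withdrawal becomes an upward step on a curve meant to show success, and that step comes earlier than any on-schedule arrival at target. Curves are drawn separately for pooled placebo, low dose and high dose, so an arm losing more children mid-ladder could appear to reach maintenance sooner. The maintenance-dose distribution would also mix settled doses with the last dose before withdrawal. There is a smaller question for by-period exposure and adverse-event tables: whether such a child's last updosing step belongs to Pre-maintenance or Maintenance.

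**Working it through.** **1. Dropout (SAP 3.2).** 48 / (1 − 0.20) = 60 children, as the plan states. At 2:2:1:1, each active arm has 60 × 2/6 = 20. Of these, 20 × 0.20 = 4 leave and 16 remain.

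**2. Calendar (Protocol Table 3, one level every 2 weeks).** Level j, with 5 mg as level 1, starts at Week 2(j − 1), Day 14(j − 1) + 1.

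| Level | Starts | Held 2 weeks by |
|---|---|---|
| 50 mg | Week 4, Day 29 | Week 6 |
| 200 mg | Week 8, Day 57 | Week 10 |
| 1500 mg (low target) | Week 16, Day 113 | Week 18 |
| 4500 mg (high target) | Week 20, Day 141 | Week 22 |

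**3. The rules applied to one child.** A low-dose child leaves at Week 10 after two tolerated weeks on 200 mg.
- The dose is at least 50 mg, so it is not set to missing.
- The last dose was tolerated for 2 weeks, so 6.2.1 is met.
- The child has discontinued the study, so 7.8.3.10 settles the dose.
- A maintenance dose exists, so the child is not censored.

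The event falls at 57 − 1 + 1 = Day 57, which is 113 − 57 = 56 days before the earliest on-schedule 1500 mg dose.

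**4. Effect on the curve (assumed example).** Take 20 low-dose children: 4 leave as above and 16 start 1500 mg at Week 16.
- SAP rule: 4/20 = 20% from Week 8, then 100% at Week 16.
- Leavers censored: 0% until Week 16, then 16 of 16 at risk have the event, so 100%.
- Discontinuation as a competing event: 0% until Week 16, then 16/20 = 80%.

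Censoring removes the false early step, but in this example the curve still ends at 100% although only 80% arrived. It does so because every remaining child reaches target.

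**5. How many children.** Assume dropout is uniform over 40 weeks and steps run on schedule. The window opens when 50 mg has been held for 2 weeks and closes when the target starts.
- Share of dropouts in the window: (16 − 6)/40 = 25% (low); (20 − 6)/40 = 35% (high).
- Children leaving in the window: 4 × 0.25 = 1.0; 4 × 0.35 = 1.4.

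How many of these meet 6.2.1 depends on how the 14 days are counted.
- *14 days required on the last level.* With a new level every 14 days, a child leaving at a random time has held the last level for less than 14 days. In whole days counted inclusively, only the 14th day qualifies, or 1/14 = 7%. That gives 1.0/14 = 0.07 (low) and 1.4/14 = 0.10 (high): about 0.1 of 20.
- *Exits at the end of a step, or the previous level credited.* All 1.0 and 1.4 count. Per child the risk is 0.20 × 0.25 = 5% and 0.20 × 0.35 = 7%. The chance of at least one is 1 − 0.95^20 = 64% and 1 − 0.93^20 = 77%. The false step averages 1.0/20 = 5 points and 1.4/20 = 7 points.
- *Ceiling.* All 4 leavers: 4 of 20.

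Real updosing need not keep to schedule. Protocol Table 6 allows a level to be extended, which makes 14 days on the last level easier to reach. The documents give no data to size this.

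**6. By-period tables.** On the second counting, at one 2-week step each, the time that could fall in either period is 2 × 1.0 = 2.0 and 2 × 1.4 = 2.8 person-weeks; the ceiling is 2 × 4 = 8. Completers' maintenance time to Week 40 is 16 × 24 = 384 (low) and 16 × 20 = 320 (high). The shares are 2.0/384 = 0.5%, 2.8/320 = 0.9% and at most 8/320 = 2.5%.

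**The case against.** The strongest reply is that the rule is deliberate and rarely applies. SAP 7.8.3.10 names study discontinuation as a point at which the dose is settled, and SAP 6.2 presents these as operational definitions. Protocol 4.1 lets subjects remain on the highest level they reach, if at least 50 mg, so maintenance below target is legitimate. With steps exactly on schedule, almost no leaver has 14 days on the last level. Early loss is visible elsewhere: in the target-dose Kaplan-Meier, attainment by visit, the swimmer plot and the disposition table.

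Much of this stands. It limits the size and means that a leaver who had settled below target should keep the event. It does not justify giving an event to a child whose next updose was still planned.

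Three stronger readings are tempting.
- A reader might infer that a quarter to a third of dropouts will be miscounted. That needs exits at the end of a step or credit for the previous level. The SAP states neither, and the wording of 6.2.1 points to the last level.
- A reader might infer that the Maintenance Period has no usable start for leavers, since its anchor is a Week 40 assessment they never had. But 6.4.3 also has the first date of the maintenance dose stored, and 7.8.3.10 uses that date. The SAP only fails to name it as the period start for leavers, and the separate programming specifications (SAP 11) may do so.
- A reader might infer harm to the efficacy result. SAP 7.8.1 makes any subject not meeting the response definition a non-responder, whatever maintenance dose is assigned.

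**Conclusion.** Wrong as written, minor. SAP 6.2.1 and 7.8.3.10 together make an event of a subject who leaves below target while still updosing, after at least 14 days on a last dose of 50 mg or more. This conflicts with the meaning of maintenance in Protocol 4.1 and SAP 3.1.

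The size is uncertain but bounded: at most 4 of 20 children per active arm, with the two expected values (about 0.1, or 1.0 and 1.4) separated by how the 14 days are counted. All of these rest on the plan's 20% dropout; the expected values also assume uniform timing and on-schedule steps.

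The outputs affected are the exploratory time-to-maintenance curve and maintenance-dose summaries, with a very small possible effect on by-period tables. Primary and secondary analyses, the target-dose Kaplan-Meier and whole-period safety results do not change.

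**What to change.** In SAP 7.8.3.10:
- Do not count as an event a subject who leaves the study before any Week 40 assessment, below the randomized target, and while updosing was still planned. Report that level as *last tolerated dose*.
- Keep the event for a subject who had already stopped updosing at a stable dose below target before leaving, as for a completer.
- Show cumulative incidence of reaching maintenance with discontinuation as a competing event.

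In SAP 6.4.3, for subjects who leave before Week 40, name the stored first-maintenance-dose date as the Maintenance Period start, and keep those who left while still updosing in Pre-maintenance.

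The cost is SAP wording, one derived flag and one changed figure. Dose levels and dates are already in use, since exposure is "based on in-clinic dosing data and the dose level of the dispensed study drug from Suvoda IRT system". The flag takes some care. SAP 6.4.3 notes that the IRT does not identify study periods directly, so the rule for whether updosing was still planned must be written down, for example from failed dose increases (6.2.6.2) and time at an unchanged level.

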6.2.2. Maximum Tolerated Dose (MTD) in DBPCFC

The MTD is specific to the food challenges. The MTD in DBPCFC is defined as the maximum single dose of a food source resulting in no dose-limiting symptoms and assessed by the investigator to have been tolerated (i.e., subject did not experience any dose-limiting symptoms). This will be determined for each food that is challenged via a DBPCFC. The MTD at the Screening DBPCFC will be used as the baseline amount of a food source tolerated.

Similarly, the eliciting dose (reactive dose) is defined as the dose given for each food source that induces the onset of dose-limiting symptoms at which the investigator stops the challenge.

6.2.3. Study/Treatment Period

The study period is the time from the date a subject or parent signed the informed consent/assent to the last day of follow-up. It includes the screening period, treatment period, and follow-up period (only for subjects who do not participate in the OLE study).

Screening Period

The screening period will be up to 12 weeks, including Screening DBPCFC(s) and other screening assessments. The first day of the screening period is the date of informed consent/assent. The last day of the screening period is the day before the date of first dose of study drug. If the subject is re-screened, the duration of the re-screen period must be within 12 weeks, even though some of the food challenges may have been conducted earlier.

Treatment Period

The treatment period will be up to 50 weeks, including 40 weeks of treatment plus up to 6 weeks for Exit Food Challenge/Week 40 (this period may be extended to up to 8 weeks if a subject requires > 6 food challenges) and up to 4 weeks of continued blinded study treatment through EOT. The treatment period will consist of pre-maintenance (including Baseline and updosing portions), maintenance, Exit Food Challenge/Week 40 Visit, and EOT as described in Section 3.1. Pre-maintenance, maintenance and Exit Food Challenge/Week 40 Visit durations will be variable per subject.

The start of the pre-maintenance period is marked by the date of Day 1 (Baseline). The start of the maintenance period is marked by the date of first dose of the sequence of maintenance doses administered closest to the first Exit Food Challenge/Week 40 Visit assessment. The Exit Food Challenge/Week 40 Visit period starts with the date of the first Week 40 Visit assessment and the end of this period is the last day of the last DBPCFC.

Follow-Up Period

Subjects who are ineligible for or do not wish to continue to the OLE study will receive instruction by the investigator about withdrawal from study drug and attend a Follow-Up Visit. The follow-up period will be 14 days from the EOT Visit. The beginning of the follow-up period is marked by the date of the EOT Visit + 1.

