Maintenance portion of the Treatment Period: Once the appropriate target dose (or highest tolerated dose) is achieved, it will be maintained until Week 40. The maintenance portion of the treatment period may range from 2 to 22 weeks. Once a subject enters maintenance (e.g., no further updosing is planned), study visits will continue at every 2 weeks; however, on-site visits can be spaced out to every 4 weeks and the other visits performed via tele-visit. Vital signs and physical examination can be skipped for these visits. The Weeks 12, 20, 24, and 38 visits must be performed on-site.

At the Week 40 visit, all subjects will undergo an Exit DBPCFC for all Reactive Foods determined during screening. The Week 40 visit will be done over multiple visits (for up to 6 weeks) to allow for adequate separation of individual DBPCFC procedures. The Exit DBPCFCs (Figure 4) will be performed in accordance with Practical Allergy (PRACTALL) guidelines (Sampson, 2012) and will require progression in an unaltered sequence, without repeating any dose. The Exit DBPCFCs will assess the same levels as done at study entry, as well as evaluating higher levels up to 4000 mg of protein of each reactive food source (see Figure 4).

In order to obtain results before the Week 40 assessments begin, subjects will have an expanded study visit at Week 38. SPTs will be performed for all 15 foods. Foods that were determined to be Non-reactive Foods at Screening will be reevaluated to assess for potential new FA development during the treatment period. Each Non-reactive Food at Screening will be assessed for any new clinical symptoms resulting from the food source; SPT results will also determine which additional foods, if any, will get an Exit DBPCFC, per Figure 4. Only positive results on the DBPCFC will define a new FA developed during the treatment period.

Subjects will continue on study drug during the Exit DBPCFC period, but the daily study drug dose will be withheld on the day of the DBPCFC (± additional days per investigator judgment).

After the final Exit DBPCFC, all subjects will continue to receive study drug at their treatment dose for up to 4 weeks in a blinded treatment extension period, followed by the End of Treatment (EOT) visit in order to maintain the blind during subject-level data cleaning. Thereafter, eligible subjects (taking either ADP101 or placebo) who complete the study (through EOT) will be

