9.4.4. Safety Analyses

All safety analyses will be performed on the Safety Population categorized by updosing and maintenance portions of the treatment period, as well as the blinded treatment extension and the follow-up periods. The safety assessment will be based on the frequency of AEs, observation of clinically significant abnormalities of laboratory values, concomitant medication use, and vital signs data in the Safety Population. Incidence rates of safety events adjusted by exposure in the maintenance dose level may also be reported.

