6.4.3. Relationship between Analysis Visit and Study/Treatment Period

There is currently no direct readily identifiable information for study periods in the Suvoda IRT system. For the purposes of analysis, in order to generate data summaries by study period as described in this SAP, these periods will be derived as a “Visit Period” variable in the analysis datasets for the study by mapping to study visits that fall into each period.

The derivation of these periods is as follows:

- **Screening Period:** This will be up to 12 weeks from the day a subject or parent sign the informed consent/assent form to screen for the study. The visit, date and data corresponding to this period will be the screening visit, date, and data from the eCRF for each data domain. For occurrence datasets such as adverse events and concomitant

medications, a start date of informed consent date and an end date 1 day prior to the Day 1 Visit in Suvoda IRT system will be used to classify data into this period. If a subject is rescreened, data from a prior screening (e.g., food challenge results) may be included although the data is outside of the screening period just prior to baseline.

- **Pre-Maintenance Period:** This period is subsequent to the Screening Period and will commence when a subject has satisfied all screening criteria and is randomized to receive the first in-clinic dosing of the study drug. The visit and date for this period will be considered the “Day 1 (Baseline)” visit and date from the Suvoda IRT system for dosing data or the baseline visit determined for each subject in other data domains. However, the end date of this period will differ per study subject resulting to different duration of this period per study subject. The end date for this period will be 1 day prior to the date of first dose of the sequence of maintenance doses administered closest to the first Exit Food Challenge/Week 40 Visit assessment. The visits, dates and data corresponding to this period will be the visits, dates and data from each data domain that falls into the start and end dates of this period. For occurrence datasets such as adverse events and concomitant medications, the events or medications recorded with the start dates that fall into the start and end dates of this period, will be classified into this period. If the duration of these events span multiple periods, they will be considered ongoing safety events.

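### The SAP dates the Maintenance Period backwards from the Exit challenge, so an adverse event that causes a dose reduction after target is reached is classified as Pre-Maintenance

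*SAP*

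**What the plan says.** Protocol 1.1 and 4.1 describe maintenance going forward in time: "Once the appropriate target dose (or highest tolerated dose) is achieved, it will be maintained until Week 40". Protocol 9.4.4 asks for safety by portion of treatment: "All safety analyses will be performed on the Safety Population categorized by updosing and maintenance portions".

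The SAP works from the other end.

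- 6.2.1 defines the maintenance dose as "the study drug dose with which the subject is last treated before the Exit DBPCFC or EOT (whichever occurs earlier) and tolerated" for two weeks or more.
- 6.2.3 opens the period at the start of the run of those doses nearest to Exit: "The start of the maintenance period is marked by the date of first dose of the sequence of maintenance doses administered closest to" the first Exit/Week 40 assessment. 6.4.3 repeats this: "The start date for this period will be the date of first dose of the sequence of maintenance doses administered closest to" that assessment. 6.2.6.1 uses the same date to split exposure.
- 6.4.3 closes the preceding period accordingly: "The end date for this period will be 1 day prior to the date of first dose of the sequence of maintenance doses".
- 6.4.3 and 7.9.1 place each AE once, in the period that contains its start date.

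Other SAP text points the other way. 6.4.3 also says Maintenance opens as soon as updosing is over. 7.7 plans to count dose decreases during maintenance as well as before it. 7.8.3.10 lets the maintenance dose be fixed at the moment target is reached. SAP Section 9, which lists changes from the protocol, does not mention a changed period definition.

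**The concern.** Dose reduction after an allergic AE is foreseen: Protocol 6.5.1 allows downdosing, and Protocol Table 6 lists reduction among the options for Grades 1 to 3. Once a reduction has happened, the SAP rule restarts Maintenance after it.

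- **Permanent reduction.** The reduced dose becomes the maintenance dose, and its run begins after the AE.
- **Temporary reduction.** The run nearest to Exit begins on return to the dose, again after the AE.

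Membership of the Maintenance Period thus depends on having no later dose change, a post-randomization condition tied to the outcome being counted. The date feeds the by-period tables of AEs, allergic events of Grade 3 or higher, AEs of special interest and exposure-adjusted rates (SAP 7.9.1). It also feeds rescue medication (7.6), epinephrine use (7.8.3.6) and accidental exposure (7.8.3.7 and 7.8.3.8). A reader of those tables wants to know how ADP101 is tolerated once target is reached, and for this class of event they cannot answer.

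**Working it through.** **Inputs from the documents.** Protocol Table 3 gives the levels 5, 20, 50, 100, 200, 400, 700, 1000, 1500, 3000 and 4500 mg, with one step every two weeks. The date rules are those of SAP 6.2.1, 6.2.3, 6.2.6.1 and 6.4.3. **Assumed:** no failed steps, and the timing and frequency of reductions, which the documents do not give.

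**Step 1: earliest arrival at target.** 1500 mg is 8 steps after the first dose, 8 × 2 = Week 16, leaving 40 − 16 = 24 weeks. 4500 mg is 10 steps, 10 × 2 = Week 20, leaving 20 weeks. The plan's own figure for maintenance is 2 to 22 weeks. The 2 reproduces (40 − 38). The 22 arises as 38 − 16 or 40 − 18; counted from first target dose to Week 40 it would be 24. Nothing below depends on this.

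**Step 2: one subject.** A low-dose subject reaches 1500 mg at Week 16 and has a dose-reducing AE at Week 30.

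| Rule | Maintenance weeks | Length | AE counted in | Weeks moved to Pre-Maintenance |
|---|---|---|---|---|
| From first target dose | 16–40 | 24 | Maintenance | 0 |
| SAP, permanent reduction | 30–40 | 10 | Pre-Maintenance | 30 − 16 = 14 |
| SAP, two weeks reduced, then return | 32–40 | 8 | Pre-Maintenance | 32 − 16 = 16 |

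**Step 3: rates.** Let a share s of subjects have at least one dose-reducing AE at a constant hazard over T weeks at target. Expected events per subject are Λ = −ln(1 − s), and the rate is Λ × 52/T per person-year. Under the SAP dates the numerator is 0, apart from the final two weeks (step 4). With permanent reductions the fraction of maintenance person-time kept is (1 − e^−Λ)/Λ = s/Λ. With a two-week reduction and return it was simulated (400,000 subjects per setting).

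| s (assumed) | Λ | Rate from target, low dose (T = 24) | Rate from target, high dose (T = 20) | SAP rate | Time kept, permanent | Time kept, two-week (low / high) |
|---|---|---|---|---|---|---|
| 5% | 0.0513 | 0.11 | 0.13 | 0 | 97.5% | 97.1% / 97.0% |
| 10% | 0.1054 | 0.23 | 0.27 | 0 | 94.9% | 94.1% / 94.0% |
| 20% | 0.2231 | 0.48 | 0.58 | 0 | 89.6% | 88.0% / 87.6% |
| 40% | 0.5108 | 1.11 | 1.33 | 0 | 78.3% | 75.2% / 74.6% |

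Exposure moves with the events, but far less than in proportion, so the smaller denominator does not make up for the lost numerator.

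**Step 4: the final two weeks.** A dose reduced less than two weeks before Exit fails the two-week condition in 6.2.1, so the SAP does not settle where that AE falls. At a constant hazard this window holds 2/24 = 8% (low dose) or 2/20 = 10% (high dose) of such events. Hence close to zero, not exactly zero.

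**Step 5: subjects who stop during updosing.** 7.8.3.10 withholds a maintenance dose only below a floor: "If a subject exits the study prior to achieving a dose of at least 50 mg, then the maintenance dose will be set to missing". It also lets the dose be determined at discontinuation. A subject who stops after two weeks at 700 mg can therefore have a maintenance dose, while the anchor for the period, the first Exit assessment, may not exist. If a period were assigned anyway, updosing events would move into Maintenance, the opposite direction.

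**The case against.** The strongest reply is that the SAP never defines a sequence of doses, and that the texts in 6.4.3, 7.7 and 7.8.3.10 suggest its authors expected decreases inside Maintenance. That is fair: an unbroken run is an interpretation. It is the better-supported one, because choosing the closest sequence presupposes more than one, and 6.2.6.1 treats downdosing as splitting a dose level into separate intervals. If the authors meant otherwise, the three start-date statements still need correcting.

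Second, Protocol 4.1 ties entry to maintenance to no further updosing being planned, so a return to target after a reduction could count as updosing. This stands as a point about the return interval. It does not move the AE that prompted the reduction, which happened at target.

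Third, a reader might infer that maintenance safety as a whole will look too clean, or that these events disappear. The documents do not support that. Whole-treatment tables keep every event. SAP 7.9.1 has an overview row and a listing for AEs leading to drug modification, and counts AEs ongoing in each period. AEs managed without a dose change in the last run, and those ending participation in that run, stay in Maintenance. Step 5 may push the other way, and no net direction has been computed.

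Fourth, a reader might infer that ADP101 is favoured over placebo. That requires reductions to be commoner on ADP101, which is plausible but for which the documents give no figure.

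Finally, Protocol 9.4 lets the SAP prevail over that section. This does not resolve the SAP's conflict with itself or with the design description in Protocol 4.1.

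**Conclusion.** The concern holds within limits. As written, the SAP's start date places reduction-causing AEs, and the time at target before them, in Pre-Maintenance, and this contradicts Protocol 4.1 and two other statements in the SAP. By-period maintenance rates of such AEs are near zero whatever the true rate. The 0.11 to 1.33 per person-year range shows only what would be missed if 5% to 40% of subjects were affected, with the fastest updosing and a constant hazard; it is not a forecast. The effect on the total maintenance AE rate, and any difference between arms, cannot be sized from the documents. Treatment of subjects who stop during updosing is a separate gap in the rule, of uncertain effect. The primary efficacy analysis and whole-treatment safety results are untouched.

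**What to change.** This changes the analysis only and leaves dosing as it is. In SAP 6.2.3, 6.2.6.1 and 6.4.3, for period classification:

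- Start Maintenance at the first dose at the randomized target. For subjects who never reach it, start at the first dose of the highest level held when updosing ends. Do not count unsuccessful increases as defined in 6.2.6.2.
- Keep later reductions and returns inside Maintenance.
- Classify subjects who discontinue during updosing as Pre-Maintenance only.
- Keep the 6.2.1 dose as an exit-dose variable for 7.8.3.10 and 7.8.3.11.

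Record the definition in SAP Section 9. If the present rule is kept, the least that is needed is a sensitivity tabulation of the by-period AE tables under the forward definition.

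The cost is reprogramming one derived variable from dose-level dates already in the IRT, with no new data, and a maintenance AE rate that will look less favourable.
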